7.3.4 DISPOSAL OF USED TEST UNITS

At the discretion of the Sponsor, all used Test Units may be collected and returned to sponsor for download of internal data and proper destruction of unit.

090177e19dd636e3Approved\Approved On: 25-Jun-2023 03:44 (GMT)

7.3.5 REFERENCE METHOD AND ADDITIONAL TESTING METHODS

Nasal swab samples are important as they provide a natural nasal matrix to conduct analytical reference testing and research. It is imperative that specimens obtained for reference testing are prepared and shipped to the reference laboratory.

Specimens should be stored refrigerated and shipped daily (within 24 hours of collection). Site staff will receive training from the Sponsor or its representative on procedures required to process specimens for shipment to the reference laboratory. Specimens should be shipped with cold packs to maintain the required temperature (2-8°C). Specimen manifest shall accompany the specimens. Inadequate documentation could result in a delay in testing and possible specimen rejection.

Upon receipt, the reference laboratory shall verify the contents of each shipment and communicate any missing or damaged contents to the Sponsor. Aliquots shall be stored for future testing to be performed both during or after the study. All results shall be communicated to the Sponsor or its representative.

Additional testing for discrepant results may be performed to investigate the discrepancy. The discrepant sample, along with some or all non-discrepant samples, may undergo additional testing.

At the end of the study, at Sponsor's discretion, all residual remnant aliquots remaining at the reference laboratory or additional testing laboratories will be sent to the Sponsor or its representative or destroyed.

7.4 RISKS AND ADVERSE EVENTS

No side effects or adverse effects are anticipated in this study. However, events that may be related to the specimen collection procedure, but result only in local, mild, and transient discomforts include (a) local, mild discomfort or "tickling sensation" in the nose, (b) sneezing, (c) slight gagging or mild irritation in the nose, (d) eye tearing or (e) minor/temporary nosebleed. These risks will not be considered AEs for this study but will be recorded in source documentation.

AEs experienced by the study staff conducting the study shall include any unintended direct contact or bodily exposure to biological fluids or specimens while performing protocol related testing. Personnel performing the test will also be instructed to report any AEs that happen during testing.

The investigator and designated study personnel shall monitor each subject for AEs during the study. AEs reported between consent and completion will be recorded in the Adverse Event Reporting Form. All AEs reported will be tabulated and reviewed during the study in accordance with the procedure for reporting AEs and SAEs.

Follow-up of AEs will occur in accordance with each individual case. Subjects shall be reimbursed for any further medical costs from any treatments or tests that arise because of an adverse event directly related to this study. All AEs reported will be tabulated and reviewed during the study in accordance with Sponsor's or its representative's internal procedures and 21 CFR 812.150 and 21 CFR 812.46.

The study consists of a single visit and there will be no follow-up. The onset for an AE or SAE experienced by a subject will be recorded from the time of signing the informed consent form and assent form, if applicable, until study completion or termination (if self-reported by the subject). The Investigator and/or designee will continue to monitor the subject with additional assessments until the event is considered resolved, stabilized, or is lost to follow-up. The date of resolution will also be recorded on the source document.

090177e19dd636e3Approved\Approved On: 25-Jun-2023 03:44 (GMT)

The full description of any AE or SAE, including the nature, date and time of onset and resolution, determination of seriousness, frequency, severity, treatment, outcome, and relationship to the study will be recorded on the Adverse Event & Serious Adverse Event Report Form.

SAEs must be reported to Lucira Health or its representative within 24 hours of the Investigator's first knowledge of the event. A completed SAE report and supporting documentation, using the form entitled "Unanticipated Event" form, shall be completed and transcribed into the EDC system within 24 hours of Investigator's first knowledge. Within this same timeframe, an email documenting knowledge of a potential SAE must be sent to Lucira Health Clinical Affairs.

A serious adverse event (SAE) is defined as any adverse event that results in any of the following outcomes:

- Death
- Life-threatening experience
- Required or prolonged inpatient hospitalization
- Persistent or significant disability/incapacity
- Congenital anomaly
- Important medical events that may jeopardize the patient or subject and may require medical or surgical intervention to prevent one of the outcomes listed above

Regulatory Reporting Requirements for Adverse Events

The Sponsor is responsible for submitting reports of SAE/UADE events to the FDA within 10 working days of the Sponsor first becoming aware of the event, and follow-ups as requested by the FDA.

IRB Reporting Requirements for Adverse Events

If a subject experiences an Unanticipated Adverse Device Event (UADE) because of this study, the Investigator must submit an Unanticipated Event Form, as per the instructions on the form, to the Sponsor within 24 hours, and the IRB within the time specified by the IRB. Incidents and deviations relating to subject safety and informed consent shall be reported to the Monitor and the IRB. All other AE must be communicated to the Monitor within 24 hours, and the Monitor will then notify the Sponsor. The Monitor shall submit to the IRB per the IRB guidelines.

8 DATA ANALYSIS AND STATISTICAL CONSIDERATIONS

8.1 SAMPLE SIZE

Clinical agreement specimen enrollment shall target 50 positive Flu A, 30 positive Flu B, and 120 positive COVID-19 until at least 1000 negative subjects are recruited to satisfy specificity requirements of $\leq 98\%$ for COVID-19 and $\leq 95\%$ for Flu A&B.

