1.1 SYNOPSIS

[figure not shown]
Protocol Title	Performance Evaluation of the Lucira COVID-19 & Flu Test as Compared to FDA cleared/authorized SARS-CoV-2 and Influenza A&B Assays
Protocol Number	09A-CLI-001
Objective(s)	The primary objective is to evaluate the performance of the Lucira COVID-19 & Flu Test as compared to FDA cleared or authorized SARS-CoV-2 and Influenza A&B Assays.
Number of Subjects	Minimum of 1000 Symptomatic subjects
Number of Sites	Minimum of 3 sites from at least 2 geographically diverse locations
Study Duration	At least 12 weeks

090177e19dd636e3\Approved\Approved On: 25-Jun-2023 03:44 (GMT)

Study Design	
This study is a prospective, multi-center study to evaluate the performance of the Lucira COVID-19 & Flu Test, a real-time RT-LAMP test intended for the qualitative detection and differentiation of RNA from SARS-CoV-2, Influenza A and Influenza B in self-collected nasal swab samples designed to report rapid test results. The Lucira COVID-19 & Flu Test will be compared with a composite reference method for the detection and differentiation of COVID-19, influenza A and influenza B virus in nasal swabs from patients with signs and symptoms of COVID-19 and/or flu-like illnesses.
 
After determining subject eligibility and following the completion of the informed consent process, each subject will receive a unique study identification number.
 
A subject's participation in this study will consist of one study visit. The subject self-collects a nasal swab sample according to Lucira COVID-19 & Flu Test instructions and runs test according to Quick Reference Instruction (QRI).
 
Following the Lucira COVID-19 & Flu Test self-collection will be an additional swab collection for reference method testing. One (1) additional NS specimen will be collected by the health care professional, prepared in Transport Medium, and sent to the reference laboratory as directed by the Study Operations Manual.
 
Each collection component (investigational product and reference method) may have a maximum of two swabs, including retests, for a maximum of four swabs per visit.

Study Population	
Subject demographics including gender, age, education level, employment status, and household income shall be collected.

090177e19dd636e3\Approved\Approved On: 25-Jun-2023 03:44 (GMT)

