2 INTRODUCTION

The Lucira COVID-19 & Flu Test is a real-time RT-LAMP test intended for the qualitative detection and differentiation of RNA from SARS-CoV-2, Influenza A and Influenza B in self-collected nasal swab samples.

The test consists of a nasal swab, a sample vial the nasal swab sample is placed in to prepare the sample for testing, and a test unit which detects whether SARS-CoV-2, Influenza A, and Influenza B virus is present within the specimen. The Lucira test uses a proprietary, molecular based detection process to detect whether a person is actively shedding the genomic RNA from the SARS-CoV-2, Influenza A, or Influenza B virus.

The purpose of this study is to investigate the Lucira COVID-19 & Flu Test for the in vitro qualitative detection and differentiation of RNA from SARS-CoV-2, Influenza A, and Influenza B in nasal swab specimens from patients suspected of COVID-19 or Influenza A or Influenza B. The primary objective is to test at least 1000 self-collected nasal swab samples for SARS-CoV-2 and Influenza A&B as compared to FDA cleared/authorized SARS-CoV-2 and Influenza A&B Assays.

Data generated collected in this study shall support an FDA and/or other notified body submission(s).

Known Potential Risks

For this study, the risks to human subjects are minimal. Furthermore, the protocol is exempt from IDE according to §812.2(c) of the IDE regulations because it:

- is non-invasive
- does not require an invasive sampling procedure that presents significant risk
- does not by design or intention introduce energy into a subject; and
- is not used as a diagnostic procedure without confirmation by another medically established diagnostic product or procedure.

090177e19dd636e3Approved\Approved On: 25-Jun-2023 03:44 (GMT)

The procedures outlined in this protocol do not involve significant risk to subject safety. Subjects will be provided the Investigator's contact information and will be instructed to notify them of any Adverse Events (AE) they experience during or secondary to specimen collection procedures. For all forms of swab collection, there is a minimal risk for visibly bloody swabs.

Known Potential Benefits

There is no direct benefit for a subject's participation.

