3.2 INTENDED USE

The Lucira COVID-19 & Flu Test is a single use real-time RT-LAMP test kit intended for simultaneous rapid qualitative detection and differentiation of RNA from SARS-CoV-2, Influenza A, and Influenza B virus from self-collected anterior nasal (nasal) Swab specimens, in individuals aged 14 years and older (self-collected), or individuals ≥ 2 years (collected by an adult) suspected of respiratory viral infection consistent with COVID-19, Influenza A, and/or Influenza B. Clinical signs and symptoms of respiratory viral infection due to SARS-CoV-2 and influenza can be similar. The Lucira COVID-19 & Flu Test is intended for use as an aid in the differential diagnosis of SARS-CoV-2, Influenza A, and Influenza B, in humans, and is not intended to detect Influenza C.

The SARS-CoV-2, Influenza A, or Influenza B RNA is generally detectable in nasal Swab samples during the acute phase of infection. Positive results are indicative of the presence of SARS-CoV-2, Influenza A, or Influenza B RNA; clinical correlation with patient history and other diagnostic information is necessary to determine patient infection status. Positive results do not rule out bacterial infection or co-infection with other viruses. The agent detected may not be the definite cause of disease.

Persons who test positive with the Lucira COVID-19 & Flu Test should seek follow up care with their physician, or healthcare provider, as additional testing and public health reporting may be necessary.

Negative results do not preclude infection from SARS-CoV-2, Influenza A, and/or Influenza B and should not be used as the sole basis for treatment or other patient management decisions. Negative results must be combined with clinical observations, patient history, and epidemiological information.

This Lucira COVID-19 & Flu Test is intended for self-testing in a non-laboratory setting, or for home use.

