4 OBJECTIVES

The primary objective is to confirm the Lucira COVID-19 & Flu Test provides similar performance to a high complexity lab molecular diagnostic RT-PCR assay(s) with known high sensitivity. The sensitivity and specificity endpoint are PPA $\geq 80\%$ /NPA $\geq 98\%$ for COVID-19 and PPA $\geq 90\%$ /NPA $\geq 95\%$ for Flu A&B.

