090177e19dd636e3Approved\Approved On: 25-Jun-2023 03:44 (GMT)

Reference lab shall receive study samples and run samples against FDA cleared/authorized approved SARS-CoV-2 and Influenza A&B Assays. Discrepant analysis samples may be run on a separate FDA cleared/authorized SARS-CoV-2 or Influenza A&B Assays.

Reference testing shall characterize specimens as negative or positive for SARS-CoV-2 and Influenza A&B. Therefore, sensitivity and specificity of the Lucira COVID-19 & Flu Test will be calculated by comparison with the reference methods.

Upon study completion, remnants should be returned to the Sponsor.

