8.3 DATA ANALYSIS

All summaries and analyses should be presented in tabular or graphical form.

➤ Analysis Sets

There will only be one analysis set consisting of samples with valid Lucira COVID-19 & Flu Test results and valid reference results. Valid Lucira COVID-19 Test results may be positive or negative for COVID-19. The percentage of the expected result shall be computed individually along with the associated 95% Wilson Score Confidence Interval for each set.

For all invalid Lucira COVID-19 & Flu Test results, one additional specimen collection should be attempted, and the Lucira COVID-19 & Flu Test should be re-run with a new Test Kit. If specimen recollection leads to a valid Lucira COVID-19 & Flu Test result, that valid retest result should be reported. If the Lucira COVID-19 & Flu Test result is "Invalid", then this test result shall be considered completely invalid and therefore non-evaluable.

➤ Prevalence Rate / Expected Values

Study prevalence of SARS-CoV-2 and Influenza A&B should be summarized by counts and percentages

➤ Collection Performance/ Incidence Rate

Relevant study observations should be summarized by counts and percentages:

- Self-Collection
- Assisted Collection

➤ Missing Values

Missing values should not be imputed for any of the study assessments.

➤ Data Exclusions

The following shall result in subjects being removed from final data analysis:

- Subject withdrawals
- Subject does not meet inclusion/exclusion criteria
- Swab specimens were not processed according to protocol
- Missing results
- Excluded by an Event

This analysis should be presented across all study sites and by individual study site.

➤ Efficacy Analysis

Sensitivity and specificity along with their associated 2-sided Wilson Score 95% Confidence Intervals will be estimated for SARS-CoV-2 and Influenza A&B on the Lucira COVID-19 All-In-One Test in comparison to the reference test using the formulas below and a 2 x 2 contingency table ([Table 13.1](#)).

090177e19dd636e3\Approved\Approved On: 25-Jun-2023 03:44 (GMT)

Positive Percent Agreement: $a/(a+c) \times 100$

Negative Percent Agreement: $d/(b+d) \times 100$

Table 13.1: 2 x 2 table for calculation of positive percent agreement and negative percent agreement:

	Reference Positive	Reference Negative	Row Totals
Lucira Positive	a	b	a+b
Lucira Negative	c	d	c+d
Column Totals	a+c	b+d	a+b+c+d

➤ **Invalid Rate**

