9.1.5 CLINICAL MONITORING

The task of the study monitor is to ensure the acceptable conduct of the study through frequent contacts by phone, email, and in person with the responsible Investigator/designee, in accordance with the Sponsor's or its representative's internal procedures.

Lucira Health will monitor study progress in accordance with the protocol and applicable regulations. To ensure equal distribution of enrolled subjects based on FDA EUA guidance and satisfy specificity requirements, enrollment will be closely monitored. Lucira Health personnel or designee may perform an audit at any time during or after completion of the study, and all data pertaining to a subject's participation and all study-related documentation in this investigation must be made available. In addition, a representative from a regulatory authority may choose to inspect a study site at any time prior to, or after completion of the clinical study. All pertinent study data shall be made available to the regulatory authority for verification, audit, or inspection purposes.

When the enrollment goal is reached, Lucira Health or its representative will notify the sites the study is complete.

The duration of the study is expected to be at least 12 weeks. When the study is ready to be terminated, a Site Closeout Visit shall be conducted. Sites will be instructed on the disposition of unused investigational materials by Lucira Health or its representative at that time. Study documents will be checked for completeness and filed. The Investigator will allow Lucira Health and/or its representative and/or any regulatory authority to inspect all CRFs and study-related documents to verify the study was performed according to protocol. Monitors will review informed consent forms for completeness as well as verify source documentation.

090177e19dd636e3\Approved\Approved On: 25-Jun-2023 03:44 (GMT)

To ensure the accuracy of data, direct access to source data by the Sponsor, its representative, and regulatory authorities is mandatory. Direct access to source data may be required to perform de-identified analysis both during and after the study. The Sponsor reserves the right to terminate the study for refusal of the Investigator/Institution to supply source documentation of work performed in the study.

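### Does the unstated unit and form of the flu PPA criterion, with no derivation for 30 Flu B positives, leave the primary verdict open?

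*Combined protocol and SAP*

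**What the plan says.** Section 4 gives the only flu success criterion: "PPA $\geq 90\%$ /NPA $\geq 95\%$ for Flu A&B". Section 8.1 sets the enrolment numbers, "shall target 50 positive Flu A, 30 positive Flu B, and 120 positive COVID-19 until at least 1000 negative subjects are recruited", and links them to the specificity requirements only. It states no expected PPA, power or precision goal.

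Section 8.3 says that sensitivity and specificity "will be estimated for SARS-CoV-2 and Influenza A&B on the Lucira COVID-19 All-In-One Test in comparison to the reference test". It defines PPA as a/(a+c) × 100 from a 2 × 2 table and attaches a two-sided 95% Wilson interval. Section 5.1 describes the reference result in similar shorthand: "Reference testing shall characterize specimens as negative or positive for SARS-CoV-2 and Influenza A&B". The intended use in Section 3.2 claims "simultaneous rapid qualitative detection and differentiation of RNA from SARS-CoV-2, Influenza A, and Influenza B virus".

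The size of the study appears in three places: the Synopsis ("Minimum of 1000 Symptomatic subjects"), Section 2 ("The primary objective is to test at least 1000 self-collected nasal swab samples for SARS-CoV-2 and Influenza A&B") and the negatives in Section 8.1. Section 9.1.5 says "To ensure equal distribution of enrolled subjects based on FDA EUA guidance and satisfy specificity requirements, enrollment will be closely monitored", and that sites are told the study is complete once an enrolment goal, not defined there, is reached.

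**The concern.** The flu criterion is half of the primary objective, and no sentence gives its unit or its form. Combining the two viruses in one phrase, with one 2 × 2 table, could be taken to mean pooling. Reporting a Wilson interval could be taken to mean that the lower limit must clear 90%. At the planned targets these readings can disagree.

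If pooling were allowed, a strong Flu A result could hide a weak Flu B result in a test sold on telling the two apart. If the lower limit were the rule, the Flu B target would be too small for any result to pass. The reference laboratory reports daily, results go to the sponsor, and the sponsor or its representative announces completion. An undefined rule and an undefined closing point could then both be settled after results are seen.

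**Working it through.** **Inputs.** Targets of 50 Flu A and 30 Flu B positives (Section 8.1); 90% PPA threshold (Section 4); PPA = a/(a+c) and two-sided 95% Wilson interval, z = 1.96 (Section 8.3). The plan gives no derivation of 30, so there is no planned figure to reproduce. True PPAs below are assumptions, and no co-infection is assumed.

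**Point estimate, each virus separately.** Flu A passes at 45/50 and Flu B at 27/30, both 90.0%. The Wilson limits are [p + z²/2n ± z√(p(1−p)/n + z²/4n²)] / (1 + z²/n). For 27/30: [0.9 + 0.0640 ± 1.96 × √(0.0030 + 0.00107)] / 1.1281 = 74.4% to 96.5%. The criterion can be met at the target, with wide uncertainty that the interval displays.

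**Lower limit.** With no misses the Wilson lower limit is n/(n + z²).
- 30/30: 30/33.84 = 88.6%, fails.
- 34/34: 34/37.84 = 89.9%, fails.
- 35/35: 35/38.84 = 90.1%, passes.

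So this rule is out of reach only below 35 Flu B positives, and 30 is a target, not a cap.

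**Pooled against separate, on the point estimate.** The pooled rule needs 72/80. Since 45 + 27 = 72, any result that passes separately also passes pooled, and the chance of disagreement is the difference between the two pass probabilities. With A ~ Bin(50, pA) and B ~ Bin(30, pB):

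| Assumed true PPA (A, B) | Pooled, P(A+B ≥ 72) | Separate, P(A ≥ 45) × P(B ≥ 27) | Difference |
|---|---|---|---|
| 95%, 95% | 0.982 | 0.962 × 0.939 = 0.904 | 0.078 |
| 98%, 98% | 1.000 | 1.000 × 0.997 = 0.997 | 0.003 |
| 95%, 85% | 0.738 | 0.962 × 0.322 = 0.310 | 0.428 |
| 98%, 80% | 0.743 | 1.000 × 0.123 = 0.123 | 0.620 |

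(Products use unrounded factors.) The reading matters little when both viruses are detected well, and a great deal when Flu B is detected poorly. The most extreme split that still passes pooled is 50/50 with 22/30: 72/80 = 90.0%, with Flu B at 73.3% (Wilson 55.6% to 85.8%).

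**Which rule does the text support?**
- *Unit.* Section 8.1 sets a separate target for each virus. The Synopsis and Section 3.2 both describe differentiating Influenza A from B. The 2 × 2 table in Section 8.3 cannot signal pooling: the same sentence covers SARS-CoV-2, which has its own threshold in Section 4 and so cannot share a table with flu. It is a template. The joint flu label is shorthand that also appears in the name of the comparator assays.
- *Form.* Section 4 places the threshold on PPA, and Section 8.3 defines PPA as a proportion. The interval accompanies the estimate. No passage sets a confidence limit against a threshold.

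**Closing point.** The Synopsis and Section 2 figures are minimums. A study that recruits 1000 negatives satisfies both, so they do not compete with Section 8.1, and the enrolment goal in Section 9.1.5 reads naturally as the Section 8.1 numbers.

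**The case for a change.** The strongest case for a change is that this is the primary criterion of a study meant to support regulatory submissions, and the natural reading is inferred, not stated. A poor Flu B result could tempt someone to pool: at assumed true PPAs of 95% and 85% the pass probability would rise from 0.31 to 0.74. Stating the rule would take a few words and no extra subjects.

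Part of this stands. The unit and form are not written out, 30 has no stated basis, and the plan does not say whether the positive targets must be met before closing. If recruitment ended at 1000 subjects and Flu B made up 2% of them (an assumption), the chance of reaching 30 would be only 0.02; at 3% it would be 0.53. If it ended at 1000 negatives, the chances would be 0.06 to 0.48 and 0.74 to 0.99, for assumed COVID-19/Flu A shares from 5%/2% to 20%/10%. The documents give no shares, so these figures do not show that a shortfall is likely.

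The rest does not carry. Pooling would run against the plan's own per-virus targets and its differentiation claim, and a reader holding the protocol would see that. The lower-limit rule, and the claim that the criterion cannot be met, come from outside the plan. Crediting a Flu B specimen read as Flu A as agreement is scoring that no passage proposes.

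**Conclusion.** No change follows. This is a gap in detail that an analyst fills sensibly from the rest of the document: one 2 × 2 table for each virus, each point estimate set against its Section 4 threshold, and the Wilson interval reported beside it. Writing that down would confirm the result already reached. Withholding a verdict for any virus that falls short of its target would be a new and debatable design choice, not a correction.

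On this reading the Flu B criterion can be met at 30 positives and has a pass probability of 0.94 if the true PPA is 95%. The price is precision: a test with a true Flu B PPA of 85% would still pass 32% of the time, and a bare pass at 27/30 leaves a lower limit of 74.4%. That is a fair trade-off for a virus that may be scarce, and the planned interval makes it visible. If fewer than 30 are found, the interval widens and shows it.

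The conclusion rests on reading Sections 3.2, 4, 8.1 and 8.3 together. A passage that set a confidence limit against 90%, or that scored the two flu viruses as one result, would reopen the point. The documents contain neither.
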